2.4.4.3 Multiplicity issues

In order to handle the multiple comparisons of the non-inferiority of SAR341402 over NovoLog/NovoRapid and then the inverse non-inferiority of NovoLog/NovoRapid over SAR341402, corresponding respectively to the primary efficacy analysis and a secondary step analysis of the primary efficacy variable, the type-I error will be controlled by the use of the sequential inferential approach. Only if non-inferiority is demonstrated, inverse non-inferiority on the mean change from baseline to Week 26 in HbA1c will be assessed. The tests for the primary endpoint (Week 26) will be performed one-sided at level $\alpha = 0.025$.

The secondary efficacy variables at Week 26 and Week 52 will be analyzed for exploratory purpose only.

2.4.4.4 Additional efficacy analysis(es)

No additional efficacy analyses are planned.

2.4.5 Analyses of safety data

The summary of safety results will be presented by treatment group on treated population.

General common rules

All safety analyses will be performed on the safety population as defined in Section 2.3.2, unless otherwise specified, using the following common rules:

- Safety data in patients who do not belong to the safety population (eg, exposed but not randomized) will be listed separately.
- The baseline value is defined as the last available value prior to the first injection of IMP. When the time of assessment is not available, the value is considered as baseline if assessment date is the date of 1st IMP intake.
- The potentially clinically significant abnormality (PCSA) values are defined as abnormal values considered medically important by the sponsor according to predefined criteria/thresholds based on literature review and defined by the sponsor for clinical laboratory tests, and vital signs (PCSA criteria are provided in the ADaM metadata and in Appendix C).
- PCSA criteria will determine which patients had at least 1 PCSA during the on-treatment period, taking into account all evaluations performed during the on-treatment period, including nonscheduled or repeated evaluations. The number of all such patients will be the numerator for the on-treatment PCSA percentage.
- The treatment-emergent PCSA denominator by group for a given parameter will be based on the number of patients assessed for that given parameter in the on-treatment period by treatment group on the safety population.
- For quantitative safety parameters based on central laboratory/reading measurements, descriptive statistics will be used to summarize results and change from baseline values by visit and treatment group. Summaries will include the last on-treatment value. The last on treatment value is defined as the value collected at the same day/time of the last dose of IMP. If this value is missing, this on-treatment value is the closest one prior to the last dose intake.
- The analysis of the safety variables will be essentially descriptive and no systematic testing is planned.

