9.2.1.1 Observation period of immunogenicity variables

- The 6-month on-treatment period is defined as the time from first injection of IMP up to Week 26 (Visit 9) or up to 1 day after the last injection of IMP whichever comes earlier.
- The 12-month on-treatment period is defined as the time from the first injection of IMP up to 1 day after the last injection of IMP.

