9.2.1.3 Immunogenicity variables definition

The following definitions will be used to identify patients with a change in AIA response during the on-treatment period (2):

- Patients with treatment-induced AIAs will be defined as patients with AIAs that developed de novo (seroconversion) following the IMP administration (ie, patients with at least one positive AIA sample at any time during the on-treatment period, in those patients without pre-existing AIA or with missing sample at baseline).
- Patients with treatment-boosted AIAs will be defined as patients AIA positive at baseline that were boosted to a significant higher titer following the IMP administration (ie, patients with at least one AIA sample with at least a 4-fold increase in titers compared to baseline value at any time during the on-treatment period, in those patients with preexisting AIA).

Patients with treatment-emergent AIA (Yes, No) will be derived as follows:

- Patients with treatment-emergent AIAs (AIA incidence) will be defined as patients with treatment-induced or treatment-boosted AIAs.
- Patients without treatment-emergent AIAs will be defined as patients without treatment induced or treatment-boosted AIAs.
- Inconclusive patients (patients who cannot irrefutably be classified as patients without treatment-emergent AIAs) will not be included in the above categories and will be listed separately.

Treatment-emergent AIAs at last on-treatment value (Yes, No) will be defined using the same definitions based on results obtained at the last on-treatment visit (ie, taking into account the closest value prior to the last dose of IMP).

The peak titer will be defined as the maximal titer observed during the on-treatment period. For patients with treatment-induced and treatment-boosted AIAs, the kinetics of AIA response will be further classified as follows:

• Transient AIA response, defined as a response detected only at one sampling time point during the on-treatment period (excluding the last sampling time point); or response detected at two or more sampling time points during the on-treatment period, where the first and last AIA-positive samples (irrespective of any negative samples in between) are separated by a period less than 16 weeks, and the patient's last sampling time point is AIA-negative.

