2.1.4 Safety endpoints

The following safety parameters will be analyzed for the main 6-month and 12-month on-treatment periods:

- Hypoglycemia (according to ADA Workgroup on Hypoglycemia) (3),
- Adverse events (AEs), serious adverse events (SAEs),
- Laboratory data,
- Injection site reactions, hypersensitivity reactions,
- Vital signs: heart rate, systolic blood pressure (SBP) and diastolic blood pressure (DBP),
- Body weight.

In case of premature permanent IMP discontinuation, the process described in Section 2.5.3 will be applied to retrieve safety assessments performed at the end of treatment visit (Visit 8000).

Safety observation period

The observation period of safety data will be divided into 3 main segments:

- The pre-treatment period is defined as the time from informed consent up to the time of the first injection of IMP.
- The 12-month on-treatment period is defined as the time from the first injection of IMP up to 1 day after the last injection of IMP.
 - The main 6-month on-treatment period is defined as the time from first injection of IMP up to Week 26 (Visit 9) or up to 1 day after the last injection of IMP, whichever comes earlier.
- The post-treatment period is defined as the time starting 1 day after last injection of IMP (after the on-treatment period).

The on-study observation period is defined as the time from first injection of IMP until the end of the study (defined as the date of end of participation).

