2.1.4.7 Immunogenicity variables

If a patient discontinues the treatment prematurely, the process described in Section 2.5.3 will be applied to retrieve immunogenicity assessments performed at the end of treatment visit (Visit 8000).

AIA assessments will be determined in a blinded fashion at a central laboratory (see study flowchart in Appendix A) using a validated anti-insulin antibody binding assay methodology. Only samples collected at least 8 hours after the last administration of mealtime insulin will be taken into account in the analysis.

Anti-insulin antibodies evaluation will consist of:

- Anti-SAR341402/ NovoLog/NovoRapid antibody positive/negative status
- Anti-SAR341402/ NovoLog/NovoRapid antibody titer
- Cross-reactivity to human insulin positive/negative status

The following definitions will be used to identify patients with a change in AIA response during the on-treatment period (see Section 2.1.4 [4]):

- Patients with treatment-induced AIAs will be defined as patients with AIAs that developed de novo (seroconversion) following the IMP administration (ie, patients with at least one positive AIA sample at any time during the on-treatment period, in those patients without pre-existing AIA or with missing sample at baseline).
- Patients with treatment-boosted AIAs will be defined as patients AIA positive at baseline that were boosted to a significant higher titer following the IMP administration (ie, patients with at least one AIA sample with at least a 4-fold increase in titers compared to baseline value at any time during the on-treatment period, in those patients with preexisting AIA). The 4-fold increase in titer corresponds to an increase of two dilution steps within the titration experiment. A single dilution difference (2-fold titer increase) is within the expected imprecision of the titration method and is therefore not considered a relevant change.

Patients with treatment-emergent AIA (Yes, No, Inconclusive) will be derived as follows:

- Patients with treatment-emergent AIAs (AIA incidence) will be defined as patients with treatment-induced or treatment-boosted AIAs.
- Patients without treatment-emergent AIAs will be defined as patients without treatment induced or treatment-boosted AIAs.
- Inconclusive patients will be defined as patients who cannot irrefutably be classified as patients without treatment-emergent AIAs. Inconclusive patients will not be included in the above categories and will be listed separately.

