Treatment-emergent AIAs at last on-treatment value (Yes, No, Inconclusive) will be defined using the same definitions based on results obtained at the last on-treatment visit (ie, taking into account the closest value prior to the last dose of IMP).

The peak titer will be defined as the maximal titer observed during the on-treatment period. For patients with treatment-induced and treatment-boosted AIAs, the kinetics of AIA response will be further classified as follows:

• Transient AIA response, defined as a response detected only at one sampling time point during the on-treatment period (excluding the last sampling time point); or response detected at two or more sampling time points during the on-treatment period, where the first and last AIA-positive samples (irrespective of any negative samples in between) are separated by a period less than 16 weeks, and the patient's last sampling time point is AIA-negative.

- Persistent AIA response, defined as a response detected at two or more sampling time points during the on-treatment period, where the first and last AIA-positive on-treatment sample (irrespective of any negative samples in between) are separated by at least 16 weeks.
- Indeterminate AIA response, defined as a response where only the last sampling time point is positive or the last 2 sampling time points are positive but separated by a period less than 16 weeks.

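### The last on-treatment value is cut off at the last dose although the on-treatment period runs one day longer, so an on-treatment sample from the next morning cannot be used

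*SAP*

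**What the plan says.** **On-treatment period.** Protocol 9.2.1.1 defines the 12-month period for immunogenicity as running "from the first injection of IMP up to 1 day after the last injection of IMP". SAP 2.1.4 uses the same end for safety ("up to 1 day after the last injection of IMP"), with the 6-month period ending at Week 26 if that is earlier. SAP 2.1.4.7 ties the AIA response definitions to that same period by cross-reference.

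**Last on-treatment value, safety.** SAP 2.4.5 gives a rule in two parts for quantitative parameters measured centrally. The first is "The last on treatment value is defined as the value collected at the same day/time of the last dose of IMP". The second is "If this value is missing, this on-treatment value is the closest one prior to the last dose intake".

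**Last on-treatment value, AIA classifier.** SAP 2.1.4.7 derives treatment-emergent AIA status (Yes, No, Inconclusive) at the last on-treatment value "based on results obtained at the last on-treatment visit (ie, taking into account the closest value prior to the last dose of IMP"). Protocol 9.2.1.3 has the same restriction: "taking into account the closest value prior to the last dose of IMP".

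**Premature-discontinuation visit.** SAP 1.4 and Protocol 10.3.4 place Visit 8000 as soon as possible after the permanent stop. Protocol 10.1 makes on-site visits morning visits. It requires fasting, with no rapid-acting insulin injected at home, at early discontinuation as well. SAP 2.1.4.7 counts an AIA sample only if it was taken at least 8 hours after mealtime insulin.

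**The concern.** The period that gives the last on-treatment value its name extends one day past the last dose, but neither rule admits a value from that day. The visit designed to capture the end-of-treatment state comes after the decision to stop. If it is held promptly, its sample falls on exactly that extra day. The sample then counts as on treatment for every any-time analysis but is passed over in the one summary meant to show the final state.

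At stake are the last on-treatment summaries of laboratory data (SAP 2.4.5.4) and the AIA classifier. The classifier is more than a table row: SAP 2.4.5.7 uses it as a subgroup factor for HbA1c change, hypoglycemia, adverse events and insulin dose. Those analyses serve the secondary objective on the relationship of AIAs with efficacy and safety. The patients affected are mainly early stoppers, for whom the final value is of most interest.

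**Working it through.** The plan states no figure on this point, so the check sets the rules side by side and reads the schedule.

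**1. The rules by date.** Let D be the date of the last IMP injection and let the sample be taken on the morning of D+1.

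- On-treatment period: runs to D+1, so the sample is on treatment.
- Safety rule: accepts D, otherwise earlier. D+1 is not eligible.
- AIA classifier: accepts only values before the last dose. D+1 is not eligible.

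SAP 2.1.4 also says "The post-treatment period is defined as the time starting 1 day after last injection of IMP", which meets the on-treatment period at the same point, but it adds that this segment comes after the on-treatment period. SAP 2.1.2 treats day +1 as included for concomitant medications other than anti-diabetic ones. Reading D+1 as on treatment is consistent with both.

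**2. The same by clock time (assumed times, illustration only).**

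| Last dose | Sample | Gap | Within 24 h | At least 8 h | Safety rule | AIA classifier |
|---|---|---|---|---|---|---|
| 22:00 | 08:00 next day | 10 h | yes | yes | no | no |
| 19:00 | 08:00 next day | 13 h | yes | yes | no | no |
| 12:00 | 08:00 next day | 20 h | yes | yes | no | no |
| 08:00 | 08:00 next day | 24 h | yes | yes | no | no |
| 00:30 | 09:00 same day | 8.5 h | yes | yes | yes | no |
| 19:00 | 08:00 two days later | 37 h | no | yes | no | no |

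The first four rows are the problem. The fifth shows that the two rules differ, because the classifier has no same-day clause. The sixth is off treatment under any definition.

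**3. What replaces the lost sample.** AIA is sampled at Weeks 0, 4, 12, 26, 40 and 52 (Protocol 9.2.1.2). Safety laboratory tests are taken at screening and Weeks 26 and 52 (Protocol 9.2.3.2.3). The maximum age is the end of the interval minus the last scheduled sample, in nominal weeks.

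| Last dose in weeks | AIA value used | Up to | Laboratory value used | Up to |
|---|---|---|---|---|
| 0–4 | none post-baseline | – | none post-baseline | – |
| 4–12 | Week 4 | 12 − 4 = 8 | none post-baseline | – |
| 12–26 | Week 12 | 26 − 12 = 14 | none post-baseline | – |
| 26–40 | Week 26 | 40 − 26 = 14 | Week 26 | 40 − 26 = 14 |
| 40–52 | Week 40 | 52 − 40 = 12 | Week 26 | 52 − 26 = 26 |

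The last two rows concern the 12-month analysis only. An unscheduled central-laboratory value, which SAP 2.5.5 allows, would shorten these gaps.

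**4. Completers.** If the recorded last dose was the day before Visit 12, the classifier falls back to Week 40 (12 weeks) and laboratory values to Week 26 (26 weeks).

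**5. Does another section repair it?** SAP 2.5.4 re-allocates Visit 8000 values to a scheduled visit for by-visit analysis, and SAP 2.5.5 admits unscheduled values. Neither moves the last-dose cut-off. SAP 2.4.3.1 ends its period at the last injection, but for exposure only.

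**6. A consequence for the AIA population.** SAP 2.3.3 admits a patient on one valid on-treatment sample. Someone who stops before Week 4 can enter solely through Visit 8000, yet that sample cannot feed the classifier.

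**The case against.** The strongest reply is that a cut-off at the last dose lies wholly inside the on-treatment period, so it is a narrower definition and not an error. The SAP does use purpose-specific cut-offs elsewhere: exposure, and anti-diabetic concomitant medication, both end on the day of the last dose. But those are stated as separate periods. Here the value is named after a period from which it excludes the last day, and no reason is given.

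Other parts of the reply stand, and they limit the point. A reader might infer more than the documents support:

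- *That the AIA sentence contradicts itself.* It does not. Its explanatory clause defines which visit is meant; the result is too narrow, not incoherent.
- *That every AIA summary is bound by the strict before-the-dose rule.* That rule is stated only for the classifier. Titers at the last on-treatment value could fall under SAP 2.4.5, with its same-day clause.
- *That the patient who stops before Week 4 is misclassified.* SAP 2.1.4.7 has an Inconclusive level, and such a patient may go there.
- *That exact hour windows decide eligibility.* SAP 2.5.3 derives the last administration by date, so the clock times above are only illustrative.
- *That completers lose Visit 12 as a matter of course.* Protocol 10.1.3.1 and SAP 1.4 place the planned end of treatment at Visit 12. Protocol 10.1 bars rapid-acting insulin at home before that visit, so an earlier last dose is possible, but its frequency is unknown.
- *That the Week 26 sample is lost because SAP 2.5.3 can set the last dose date to the Week 26 visit.* That convention is given for treatment duration, not for the classifier.

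**Conclusion.** Wrong as written, with low impact. An on-treatment sample from the day after the last dose cannot be the last on-treatment safety value, nor feed the AIA classifier. The replacement is older by up to 8 to 14 weeks for AIA and up to 26 weeks for laboratory tests, or there is no scheduled post-baseline value. In the classifier the patient may then become Inconclusive.

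The effect is confined to descriptive and exploratory analyses. The primary HbA1c analysis does not use this value. Any-time AIA incidence, peak titer and potentially clinically significant abnormalities are taken over the whole on-treatment period, so the sample still counts there.

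The conclusion assumes that Visit 8000 takes place the day after the last dose and that this day is on treatment. The documents say only that the visit is held as soon as possible, so the share of patients affected cannot be derived. The ages above are maxima at nominal weeks, not expected values.

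**What to change.** In SAP 2.4.5 and SAP 2.1.4.7, define the last on-treatment value once, for safety and AIA including the classifier, as the last valid value within the SAP 2.1.4 on-treatment period. For the 6-month analyses it should be no later than Week 26. Apply it by date, in line with how SAP 2.5.3 dates the last administration, and say that the day after the last dose is included. For AIA, valid keeps the existing 8-hour condition. Samples later than that day stay excluded.

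Align Protocol 9.2.1.3 at the next amendment; a separate one is not warranted, since Protocol section 15 requires ethics committee approval for each. The cost is a few sentences and the matching derivation, with no new data or visits. It should be settled before the 6-month database lock, when treatment allocation enters the database.

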2.4.5.1 Analyses of Hypoglycemia

All analyses of hypoglycemia will be performed on the safety population and for the T1DM patients (except for analyses monthly, by time of the day and by subgroup), separately on events occurring during the main 6-month on-treatment period and during the 12-month on-treatment period (as defined in Section 2.1.4).

Incidence of patients with at least one hypoglycemia

- Incidence of patients with at least one hypoglycemia will be presented by treatment group for any hypoglycemia and for each hypoglycemia category (as described in Section 2.1.4.1).
- For any hypoglycemia, severe and documented symptomatic hypoglycemia category, incidence of patients with at least one hypoglycemia will be compared for SAR341402 versus NovoLog/NovoRapid using a logistic regression method. The model will include fixed-effect terms for treatment group, the randomization strata of geographical region and type of diabetes (Europe T1DM, US T1DM, US T2DM, Japan T1DM), screening HbA1c (<8%, ≥8%), and prior use of NovoLog/NovoRapid (Yes, No). If the logistic model does not converge (e.g., due to sparse data), randomization strata may be adapted or removed from the model. Odds-ratios and 95% CIs will be displayed using forest plots.
- Incidence of patients with at least one severe hypoglycemia will be summarized by symptom.
- The number of severe hypoglycemia and the number of documented symptomatic hypoglycemia <3.0 mmol/L (54 mg/dL) per patient will be summarized by treatment group.
- For any hypoglycemia, severe and documented symptomatic hypoglycemia category, incidence of patients with at least one hypoglycemia will be summarized by time of the day. Histograms will be provided.
- For any hypoglycemia, severe and documented symptomatic hypoglycemia category, incidence of patients with at least one hypoglycemia will be presented by subgroup and compared between SAR341402 and NovoLog/NovoRapid using a similar logistic regression model as described above, with added fixed-effect terms for the subgroup and the subgroup-by-treatment interaction. When the subgroup considered will be equal (or close) to one of the randomization strata, this randomization stratum will be removed from the model. Odds-ratios and 95% CIs will be presented across subgroups using forest plots. The significance level of the subgroup-by-treatment interaction will be also provided for descriptive purpose. The following subgroups will be displayed:
 - Race (American Indian or Alaska Native, Asian, Black or African American, Native Hawaiian or Other Pacific Islander, White, More than One Race, Unknown or Not Reported),
 - Ethnicity (Hispanic or Latino, Not Hispanic or Latino, Unknown /Not Reported),
 - Age group (<65, \geq 65 to <75, \geq 75 years of age),
 - Sex (male, female),

- Baseline BMI ($<30, \ge 30 \text{ kg/m}^2$),
- Baseline estimated GFR categories (<60, ≥60 mL/min/1.73m²),
- Randomization stratum of type of diabetes (T1DM, T2DM),
- Randomization stratum of screening HbA1c (<8%, $\geq8\%$),
- Randomization stratum of prior use of NovoLog/NovoRapid (Yes, No),
- Type of comparator (NovoLog, NovoRapid),
- Regions (North America, Western Europe, Eastern Europe, ROW),
- Duration of diabetes (<10, ≥10 years).

The analyses of hypoglycemia by type of comparator (NovoLog, NovoRapid) will also be performed on the T1DM patients.

Further subgroup analyses may be performed if deemed necessary for interpretation of results.

Number and rate of hypoglycemia per patient-year

- Number and rate of hypoglycemia per patient-year (computed as 365.25 x [total number of episodes of hypoglycemia] / [total number of days exposed]) will be summarized by treatment group for any hypoglycemia and for each hypoglycemia category (as described in Section 2.1.4.1). Non classified hypoglycemia will be displayed.
- For any hypoglycemia, severe and documented symptomatic hypoglycemia category, incidence of patients with at least one hypoglycemia will be summarized over time using Nelson-Aalen estimates. Figures will be provided.
- For any hypoglycemia, severe and documented symptomatic hypoglycemia category, number and rate of hypoglycemia per patient-year will be presented by time of the day. Histograms will be provided.
- For any hypoglycemia, severe and documented symptomatic hypoglycemia category, number and rate of hypoglycemia per patient-year will be compared for SAR341402 versus NovoLog/NovoRapid using an overdispersed Poisson regression model with a log-link function, and the logarithm of the treatment-emergent period as offset (using PROC GENMOD). The dispersion parameter will be estimated by Pearson's chi-square statistic divided by its degrees of freedom (option SCALE=PEARSON). The model will include fixed-effect terms for treatment group and randomization strata of geographical region and type of diabetes (Europe T1DM, US T1DM, US T2DM, Japan T1DM), screening HbA1c (<8%, ≥8%), and prior use of NovoLog/NovoRapid (Yes, No). If a model does not converge (eg, due to sparse data), the randomization strata may be adapted or removed from the model. Rate ratios and 95% CIs will be displayed using forest plots.

• For any hypoglycemia, severe and documented symptomatic hypoglycemia category, the number and rate of hypoglycemia per patient-year will be presented by subgroup type of comparator (NovoLog, NovoRapid) and compared between SAR341402 and NovoLog/NovoRapid using a similar overdispersed Poisson regression model as described above. If a model does not converge (eg, due to sparse data), the randomization strata may be adapted or removed from the model. Rate ratios and 95% CIs will be displayed using forest plots.

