2.1.4.1 Hypoglycemia

All hypoglycemia will be reported by patient in e-diary, transferred to the dedicated hypoglycemia event page in the e-CRF and reviewed by the investigator in specific items, or directly completed in another dedicated hypoglycemia event page in the e-CRF by the investigator. For the analyses, the investigator items will be used when available.

All hypoglycemia will be categorized according to the ADA definitions (3) as described below:

- Severe hypoglycemia: Severe hypoglycemia will be derived as an event requiring assistance of another person to actively administer carbohydrate, glucagon, or other resuscitative actions.
- **Documented symptomatic hypoglycemia:** Documented symptomatic hypoglycemia will be derived as an event with symptoms of hypoglycemia and with a measured plasma glucose concentration less than or equal to 3.9 mmol/L (70 mg/dL).
- Asymptomatic hypoglycemia: Asymptomatic hypoglycemia will be derived as an event without symptoms of hypoglycemia but with a measured plasma glucose concentration less than or equal to 3.9 mmol/L (70 mg/dL).
- **Probable symptomatic hypoglycemia:** Probable symptomatic hypoglycemia will be derived as an event with symptoms of hypoglycemia and missing plasma glucose concentration.
- **Relative hypoglycemia:** Relative hypoglycemia (recently termed "pseudohypoglycemia") will be derived as an event with symptoms of hypoglycemia but with a measured plasma glucose concentration greater than 3.9 mmol/L (70 mg/dL).

Any technical details to categorize hypoglycemia in case of missing hypoglycemia information are described in Section 2.5.3.

Hypoglycemia will be evaluated regardless the time of onset during the day.

In addition to the threshold of plasma glucose of less than or equal to 3.9 mmol/L (70 mg/dL), documented symptomatic hypoglycemia and asymptomatic hypoglycemia with a measured plasma glucose concentration less than 3.0 mmol/L (54 mg/dL) will also be analyzed.

Hypoglycemia observation period

- Pre-treatment hypoglycemia are events that occurred during the pre-treatment period.
- Treatment-emergent hypoglycemia are events that occurred during the on-treatment period (see Section 2.1.4).
- Post-treatment hypoglycemia are events that occurred during the post-treatment period.

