- Serious TEAEs: descriptive statistics by primary SOC, HLGT, HLT, and PT, showing number (%) of patients sorted by SOC internationally agreed order. The other levels (HLGT, HLT and PT) will be presented in an alphabetic order.
- Injection site and hypersensitivity reactions: descriptive statistics by PT, showing number (%) of patients sorted by decreasing incidence of PT in the SAR341402 group.
- Change in daily insulin doses (basal, mealtime, total) as defined in Section 2.4.3.1.

In order to assess the impact of pre-existing antibodies that may cross-react with SAR341402, the above parameters will also be summarized by AIA status at baseline (Positive, Negative).

The relationship between the AIA titer and the efficacy and safety assessments will be explored using scatter-plots of the peak AIA titer versus the parameters below for patients from the AIA population with titer available:

- Primary efficacy endpoint (change in HbA1c from baseline to Week 26) (for the main 6-month analyses) and change in HbA1c from baseline to Week 52 (for the 12-month analyses)
- Change in total insulin dose (U/kg) from baseline to Week 26 (for the main 6-month analyses) and to Week 52 (for the 12-month analyses)
- Rate per year of treatment-emergent hypoglycemia during the on-treatment period (severe hypoglycemia, documented symptomatic < 3.0 mol/L [54 mg/dL])
- Presence/absence of treatment-emergent hypersensitivity reactions during the on-treatment period

• Presence/absence of treatment-emergent injections site reactions during the on-treatment period

The scatterplots will also be presented separately for patients with treatment-emergent AIAs.

Listings of baseline characteristics, insulin doses, HbA1c, hypoglycemia, hypersensitivity reactions, and injection site reactions will be provided for patients with treatment-emergent AIAs and high AIA titers (AIA 'outliers' as defined above).

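### No hypoglycemia outcome defined by measured low glucose alone is compared between arms, although symptom reports in this open-label trial are unblinded

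*SAP*

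**What the plan says.** SAP 2.1.4.1 sorts events into five categories. Severe events are defined by the need for another person's help. Documented symptomatic and asymptomatic events share the ≤3.9 mmol/L limit and differ only in whether symptoms were reported. The other two need no low reading:

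- Probable: "Probable symptomatic hypoglycemia will be derived as an event with symptoms of hypoglycemia and missing plasma glucose concentration".
- Relative: "derived as an event with symptoms of hypoglycemia but with a measured plasma glucose concentration greater than 3.9 mmol/L (70 mg/dL".

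For the lower threshold the same section says that "documented symptomatic hypoglycemia and asymptomatic hypoglycemia with a measured plasma glucose concentration less than 3.0 mmol/L (54 mg/dL) will also be analyzed". It names two rows and no combined one.

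SAP 2.4.5.1 tabulates incidence and rate by arm for every category. Model-based comparison is narrower. The logistic model is specified as "For any hypoglycemia, severe and documented symptomatic hypoglycemia category, incidence of patients with at least one hypoglycemia will be compared". For the same three outcomes, "number and rate of hypoglycemia per patient-year will be compared for SAR341402 versus NovoLog/NovoRapid using an overdispersed Poisson regression model". The subgroup models, the Nelson-Aalen curves and the antibody-status comparison (SAP 2.4.5.7) do not go beyond these three.

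Outside the basic rows, the 3.0 mmol/L threshold is used only for symptomatic events. It appears in the per-patient counts ("The number of severe hypoglycemia and the number of documented symptomatic hypoglycemia <3.0 mmol/L (54 mg/dL) per patient will be summarized by treatment group") and in the antibody scatterplots ("Rate per year of treatment-emergent hypoglycemia during the on-treatment period (severe hypoglycemia, documented symptomatic < 3.0 mol/L [54 mg/dL").

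**The concern.** The trial is open-label, and patients enter their symptoms in an e-diary (protocol 9.2.3.2.1.1). The blinded laboratory measurements listed in protocol 8.3.1 are HbA1c, FPG and antibodies. Nothing there protects a symptom report.

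If knowing the arm changes how readily symptoms are reported, events move between documented symptomatic and asymptomatic. Only the first is modelled, so its odds ratio and rate ratio move with no difference in glucose. Such relabelling leaves *any* and *severe* unchanged. *Any* is still not a glucose-confirmed check, because events without a measured low value are counted in it and can dilute a real difference.

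Hypoglycemia is the main harm of an insulin. A reader comparing a new insulin aspart with the marketed one will want at least one compared measure that does not depend on the symptom label.

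**Working it through.** **1. The three modelled outcomes against two requirements.** *Any* is read here as all recorded events; SAP 2.1.4.1 gives it no separate definition.

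| Modelled outcome | Needs a measured low value? | Independent of reported symptoms? |
|---|---|---|
| Any | No: includes probable and relative events | Unmoved by relabelling of low readings |
| Severe | No: defined by assistance | Not defined by the symptom label |
| Documented symptomatic | Yes | No |

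No outcome meets both requirements. The documents state no power, margin or event rate for hypoglycemia, so there is no plan figure to reproduce. The steps below rest on assumed values.

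**2. Effect of relabelling.** Suppose the arms have equal rates of low-glucose events, and symptoms are reported for a share s0 of events in one arm and s1 in the other.

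- Documented-symptomatic ratio = s1/s0: 0.66/0.60 = 1.10; 0.70/0.60 = 1.17.
- Asymptomatic ratio = (1−s1)/(1−s0): 0.34/0.40 = 0.85; 0.30/0.40 = 0.75.
- Ratio for all measured-low events = 1.00.

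**3. How often this would look like a real difference.** Simulation of 4,000 trials per setting:

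- 290 patients per arm, 0.5 year, 4, 8 or 16 low-glucose events per patient-year in both arms.
- Between-patient variation by a gamma frailty of shape 0.5 or 1.
- Symptomatic events drawn binomially from each patient's events.
- Rate ratio with a Pearson-scaled Poisson standard error and the treatment term only (strata omitted).

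| Outcome | Median rate ratio | 95% CI excludes 1 |
|---|---|---|
| Documented symptomatic, 60% vs 66% | 1.094–1.103 | 10.7–18.9% |
| Documented symptomatic, 60% vs 70% | 1.163–1.169 | 20.3–40.4% |
| All measured-low events | 0.995–1.004 | 4.2–5.6% |

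A repeat run gave 10–18%, 19–41% and 4–6%, which agrees within simulation error.

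**4. Why *any* is a weak substitute.** Let r be the share of *any* events in the comparator arm without a measured low value, with no arm difference in those events. A true measured-low rate ratio of 1.30 then appears as (1−r)×1.30 + r:

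- r = 0.1: 1.27
- r = 0.2: 1.24
- r = 0.3: 1.21

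**5. What the planned tables can give.** Crude event rates for the symptomatic and asymptomatic rows can be added. Patient incidence cannot, because one patient can be in both rows. Suppose 50% of patients have a symptomatic and 30% an asymptomatic event. With a shared gamma frailty of shape k, the proportion with neither is (0.50^(−1/k) + 0.70^(−1/k) − 1)^(−k). The proportion with either is then:

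- k = 0.25: 0.522
- k = 0.5: 0.555
- k = 1: 0.588
- k = 2: 0.614
- independence: 1 − 0.50×0.70 = 0.65

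So the level could be about 52% to 65%. This shows only that it cannot be read from the rows; it does not say that the arms differ by that much. A model-based ratio with a confidence interval cannot be obtained from the printed rows either.

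**The case against.** The strongest reply is that the missing piece is small.

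- **Every category is shown by arm.** This includes symptomatic and asymptomatic events at both thresholds. Pure relabelling would show as one row rising and the other falling by the same number of events. This stands for crude rates. It does not supply a combined patient incidence or an interval.
- ***Any* is modelled and does not move with relabelling.** This also stands. The dilution in step 4 is modest as a point estimate and assumes a share of unconfirmed events. Dilution does cost power, though: in a simulation of the same kind, detection of a true 1.30 fell by about 7 percentage points at a 10% share and 21–25 points at 30%.
- **The size of the bias is assumed.** Correct. Both arms inject insulin aspart, all patients had used a rapid-acting analog, and the documents suggest no direction for a reporting difference.
- **The investigator reviews events, and the investigator's entries take precedence** (SAP 2.1.4.1). The investigator is also unblinded, so this does not protect the symptom label.
- **A combined measure depends on how often patients test,** and the unblinded investigator can ask for more testing (protocol 9.2.2.2.3). This stands. The measure removes one source of bias and leaves another.
- **The analyses are exploratory.** Protocol 11.4.3.1 leaves the choice of categories to the SAP, and SAP 2.4.5 plans no systematic testing. This limits the weight of the point. However, the SAP already models three outcomes, so the question is only which outcomes to model.

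Protocol 9.2.3.2.1 describes the analysis below 3.0 mmol/L without mentioning symptoms. The SAP covers it in two rows, so this is not a contradiction, but a combined row would match the protocol more directly.

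**Conclusion.** The point holds as an inexpensive improvement. None of the modelled hypoglycemia outcomes is both glucose-confirmed and independent of symptom reports, and the planned tables cannot supply the combined incidence or a ratio with a confidence interval.

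Under the assumed 6- to 10-point difference in symptom reporting, the documented-symptomatic rate ratio would be about 1.10 to 1.17 with no difference in measured glucose. Its interval would exclude 1 in about 11% to 40% of trials. These figures rest on assumed event rates, frailty and reporting shares; they are not a prediction that reporting will differ. The reading of the SAP text needs no such assumption. The primary HbA1c analysis is not touched.

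**What to change.** In SAP 2.1.4.1, define two further categories: any event with measured plasma glucose <3.0 mmol/L, and any event with measured plasma glucose ≤3.9 mmol/L. Both apply regardless of symptoms and include severe events that have a qualifying value.

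In SAP 2.4.5.1, add both to the incidence and rate tables, to the existing logistic and overdispersed Poisson models, and to the forest plots, for the 6-month and 12-month periods. Keep every planned category. State that the combined measures remove symptom-labelling bias but not bias from unequal self-testing. Make the change before the 6-month database lock, so that the measures are not chosen after results by arm are known.

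The cost is SAP wording, a few table rows and a few model runs. The e-diary already prompts for an entry on each transferred value ≤3.9 mmol/L, with or without symptoms (protocol 9.2.2.2.3), so no new data, visits or patients are needed. The downside is slightly more exploratory output.
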